10.3.4. Data entry

Field-based users will be able to access REDCap either through a classical Internet-connected tablet or computer, or through the REDCap mobile App application.

The mobile App also enables offline data entry through a tablet or an Android mobile phone. In such a case, the tablet or mobile phone will be brought by the CRA to the country CTU and further synchronized with the central database once connected to the Internet (Figure 2).

Tablets will be purchased locally by country CTUs. Configuration of tablets will be managed by the international data manager.

Figure 2: Secure data flow

Main data transfer

Coptional data transfer in case main data transfer is unavailable

Project Managers from country CTUs will be in charge of training the relevant study staff for data collection and issuing of electronic data queries for quality control. The investigator is responsible for ensuring that all sections in the eCRF are completed correctly and that entries can be verified against source data. If the investigator authorizes other persons in their staff to make entries on the eCRF, the names, positions, and signatures must be documented in writing. eCRF must be completed during/after each study visit. Any person entering data in the eCRF must be trained beforehand and appointed to do this task.

10.3.5. Data coding

The Anatomical Therapeutic Chemical (ATC) system will be used for drug classification and coding. As part of safety monitoring, AEs will be coded using the Medical Dictionary for Drug Regulatory Affairs (MedDRA, version 17.1). Coding will be performed by country CTUs based at TB-Speed consortium members institutions.

10.3.6. Data transfer

Individual patient data will be transferred from tablets to the server located at UBx using a secure file transfer protocol (ftps) with individual authentication and data logging.

CXRs (.dicom files) and Ultra test result files exported from GeneXpert (.gxx files) will be transferred to the international CTU central server using a secure web transfer (ftps). In case implementing sites experience web access issues, transfer of CXRs and Ultra result files will be done 1/ by GSM with a tablet (equipped with a SIM card) from the implementing sites to the country CTU, and 2/ from the country CTU to the international CTU central server via a secure web transfer (ftps).

In the context of the Covid pandemic, due to travel restrictions, remote site monitoring visits might be conducted by the international CTU. Where needed, pseudonymized source documents will be forwarded by the country CRA through a ftps for monitoring purpose only; source documents will be destroyed afterwards.

10.4. Description of the data verification, validation and processing (data management)

A data management plan (DMP) will be established and validated by the study coordination team at UBx. Verification of the completeness and consistency of the data is performed for all key data as well as a list of additional data defined in the DMP.

A data management system (DMS) will be developed at UBx to enable generation of standardized lists of data management queries at country level. Queries will be programmed by the international data manager for data completeness, integrity and consistency as defined in the DMP. They will be run on an at least monthly basis at the country level. Data management checks will be implemented at central level on a monthly basis. If needed, centralized correction queries will be sent by the international coordinating CTU to the country CTU, and by the country CTU to study sites. At country level, queries will be managed by the country data manager or CRA. Queries will be solved by data managers along with the country CRA.

The investigator, co-investigators, head of laboratory must allow access to relevant hospital, laboratory or clinical records, to confirm their consistency with the CRF entries. All research staff working in the study, including study nurses, national CTU team (PMs, CRAs), PIs, international coordination team (CRA, Trial Manager, Coordinating Investigators) will sign a confidentiality agreement with regards to access to individual patient data and medical records.

Central statistical monitoring will also be implemented by the international coordinating CTU to look at variables for which distributions differ from the rest of the observed data at the country, site or patient level. Its purpose is to highlight systematic (non-random) faults in filling the CRF data, protocol compliance, AEs, and to guide targeted monitoring. Variables subject to statistical monitoring are specified in the monitoring plan. Comparison of distributions is made by statistical tests or models.

Before final database freezing, a final data review will be conducted and remaining issues will be adjudicated. Closure of the database will be performed by the international data manager.

10.5. Length of data retention, archiving conditions and management

All data will be stored in a server hosted by the CREDIM (*Centre de Recherche et Développement en Informatique Médicale*) at UBx and will be declared to the French data protection authority CNIL (*Commission Nationale de l'Informatique et des Libertés*) in accordance with French regulations on personal data protection.

The server is located in a secure computer room. The network is protected by uninterrupted power supply firewalls and up-to-date viruses and malwares scanning softwares. Data backups are performed regularly. Reading, entry, modification or deletion of data will be granted via the standard authentication and access-control features.

Medical records will be stored in the clinical sites as per standard practices. Electronic data and files will be maintained on password-protected computers. Essential study documents will be retained at the coordinating centre for 15 years.

No displacement or destruction of data will be done without the agreement of the sponsor. At the end of the regulatory archiving period, the sponsor will be consulted for destruction.

10.6. Study documents archiving conditions and management

Essential documents and study records will be kept secured for 15 years after study completion, under the responsibility of each country investigator, the international CTU, and the sponsor.

Study documents constituting the Trial Master File (TMF) will be made available online to investigators on a secured website. The international coordinating CTU will be responsible for routinely updating global documentation on the study website. Country CTUs will be responsible for routinely updating national documentation on the study website.

Investigators will ensure that study records are not disposed of or removed from the study sites or the country CTU without prior notification and approval from the sponsor or his representative.

Each investigator will keep a hard copy of original documents whenever those are manually signed or generated. This includes, at site level, medical records (source documents) and study ID assignment log which are subjected to professional secrecy and confidentiality, and task delegation lists.

Data, documents, reports and SOPs should be available to be audited or inspected at any time.

11. TB-SPEED COVID SUB-STUDY

11.1. Background and rationale

Since December 2019, a novel coronavirus emerged in Wuhan, Hubei province, China and has rapidly spread to the rest of the world, becoming a pandemic [58], [59]. The WHO has named it "2019 novel coronavirus" (2019-nCoV or SARS-CoV-2) and has declared Covid-19 a pandemic and public health emergency of international concern. This is the 3rd coronavirus epidemic of large public health threat after the severe acute respiratory syndrome (SARS-CoV-1) and the Middle East respiratory syndrome (MERS-CoV) [60], [61]. Community transmission of SARS-Cov-2 virus has been reported in many African countries, with figures on cases and deaths likely to be underestimated due to the limited access to tests. As of June 23, 2020, there were 797 and 1430 cases reported in Uganda and Zambia, respectively⁴.

Children are largely untouched by Covid-19. Data from China, the United States (US) and Italy showed that only about 2% of all cases were children [62]–[66]. First data from Africa show than only 2.5% of cases were young children below the age of 5 years [66], [67]. No racial predilection has been observed in children, although emerging US data in adults suggest that minority communities may be affected disproportionately [68]. Despite the worldwide spread, the epidemiological, clinical, therapeutic and evolutionary patterns of Covid-19 remain largely unclear among children. In the largest Chinese paediatric case series to date, of 2 143 subjects, children younger than 5 years old represented 40% of all paediatric cases and 60% of the severe cases [69]. In this study, there were more boys (56.6%) than girls. Slight male predominance was also seen in the US data [70]. Few neonate cases have been reported and no cases of intra-uterine transmission was notified [71]. The median incubation period in children is usually 3 ~ 7 days (range of 1-14 days) [72].

Covid-19 has been diagnosed using real-time RT-PCR assays for 2019-nCoV nucleic acids [73], [74] on nasal swabs, sputum, lower respiratory tract secretions, stool, and blood. Few paediatric cases with negative respiratory samples were diagnosed using stool samples, on which RT-PCR is usually less sensitive [75]. Two study in French children reported similar SARS-CoV-2 viral loads in children than in adults that SARS-CoV-2-positive children exhibited viral loads that do not differ significantly compared to those of adults [76] [77]. Clinical diagnosis has also been proposed using a combination of at least two symptoms, laboratory tests and chest X-ray findings [78], [79]. Chest radiography and computed chest tomography show in the early stage of disease, multiple small plaques and interstitial changes, which are obvious in the lung periphery, that further deteriorate to bilateral multiple ground-glass opacity and/or infiltrating shadows. Lung consolidation may also occur in severe cases.

Immunological assays for SARS-Cov-2 infection will be useful to assess seroprevalence and seroconversion of infected people. The Institut de Recherche pour le Développement (IRD) has developed a high throughput serological screening assay using the Multiple Analyte Profiling (xMAP) technology (Luminex Corp. Austin, TX, USA). The assay was evaluated on a panel of well documented positive and negative samples (IgG and/or IgM antibodies) obtained from reference laboratories in Europe and collaborators [80]. It is also developed for IgM

⁴ Source: COVID-19 Dashboard by the Center for Systems Science and Engineering (CSSE) at Johns Hopkins University.

antibodies to SARS-CoV-2 to allow detect recent infections on plasma, whole blood, DBS, saliva and faecal samples.

Although epidemiological and clinical data from China, Europe, and the US show that children, and notably those aged less than 5 years, are less affected by the Covid-19 than adults, we do not know what happens when SARS-Cov-2 infection occurs in children with comorbidities affecting their immune response. This includes malnutrition that is common in low/moderate income countries in Sub-Sahara Africa, and that can be associated with other frequent comorbidities like HIV infection. Additionally, children with sickle cell disease (SCD) who present viral respiratory infection may have an increased risk of bacterial sur-infection and therefore worsening of the clinical presentation as shown in a small study of children with sickle cell disease and H1N1 influenza viral infection [81].

This sub-study will assess the prevalence and impact of the Covid-19 in young children hospitalized with severe acute malnutrition. The sub-study findings are expected to guide policy makers and clinicians on potential specific screening and management measures for this vulnerable group of children. In addition, the evaluation of the primary objective of the TB-Speed SAM study relies on clinical case definitions for the retrospective classification of children (as confirmed, unconfirmed or unlikely TB), which are based on several parameters including clinical presentation and outcome. In the context of the Covid-19 pandemic, it is therefore very important to identify SARS-CoV-2 infections at enrolment in the study and during follow-up based on clinical evolution.

11.2. Sub-study objectives

- To assess the prevalence of Covid-19 (confirmed and probable cases) in children below 5 years hospitalized with SAM
- To assess the impact of SARS-CoV-2 infection on the clinical outcomes of children with SAM
- > To describe the clinical, laboratory, and radiological characteristics of Covid-19 cases
- To assess the yield of stool as compared to naso/oropharyngeal swab for the detection of the SARS-CoV-2 by real time RT-PCR
- To assess seroprevalence and seroconversion (IgM and IgG to SARS-CoV-2) at Day 0 and Month 6

11.3. Case definition

Confirmed and probable cases are defined according to WHO Covid-19 technical guidance [82].

Confirmed case: A person with laboratory confirmation of Covid-19 infection, irrespective of clinical signs and symptoms (using nucleic acid amplification tests such as RT-PCR).

> Probable case:

- $\circ~$ A suspect case for whom testing for the Covid-19 virus is inconclusive OR
- A suspect case for whom testing could not be performed for any reason

See detailed definitions of *suspect case* per country in Appendix 6.

11.4. Sub-study population

- All children enrolled in the TB-Speed SAM study accepting enrolment in the Covid sub-study

11.5. Sub-Study design

[figure not shown]
This will be an observational sub-study nested in the TB-Speed SAM study. At the time of enrolment in the main TB-Speed SAM study, patients will be also offered to participate to the Covid sub-study. Children will be tested for SARS-Cov-2 on the day of enrolment. The duration

of enrolment in the sub-study will be of 6 months in total. Duration of follow-up for a particular participant will be 6 months, as in the main SAM study.

For hospitalised children with SAM presenting respiratory symptoms or signs, the detection of SARS-Cov-2 is routinely done in both countries and used for case management. For others, it will be done for the purpose of the study only.

The study scheme of the nested Covid-19 study is presented in Figure 3 below.

• Sample size

There is no sample size calculated. All children consecutive enrolled in the TB-Speed SAM study will be invited to participate to the Covid Sub-study.

• Statistical analysis

Prevalence (and 95% CI) of SARS-CoV-2 infection at enrolment will be calculated. Summary statistics of patient characteristics will be described. Differences in patients' characteristics between SARS-Cov-2 infected and non-infected patients will be assessed using Chi-square, Student's t-test or Wilcoxon rank-sum test as appropriate. Bi- and multivariate analysis will be used to identify effect of the Covid-19 disease on the children's outcomes. Factors associated with children's outcomes will be also analysed.

A preliminary analysis of prevalence and outcomes will be performed at 3 months (mid-study) and discussed with the SAB in order to support case detection and management decision.

11.6. Management of Covid-19 cases

At each study site, management of Covid-19 cases will follow national recommendations (see Appendix 6). This will require isolation of cases and potential antiviral treatment in addition to the standard care for SAM, as well as TB diagnosis on NPA, stool and GA as part as study procedures. Prescription of specific treatment against Covid-19 will be decided by site clinicians in accordance with country guidelines, subject to modification during the study implementation period.

As soon as a child will be identified as a Covid-19 case, the disease control team at site level will be informed in order to ensure that contacts are traced and additional suspect cases tested and isolated according to the national policy.

In the event that a child is transferred to a Covid isolation centre, study staff will ensure compliance and continuity of the main TB-Speed SAM study procedures and follow-up visits, including appropriate TB diagnosis and timely access to TB treatment if needed.

11.7. Sub-study procedures

As part of the overall informed consent process of the TB-Speed SAM study, parent(s)/guardian(s) will be informed about the Covid sub-study (see Appendix 6). Participation in the Covid sub-study will be proposed on a prospective basis to children newly enrolled in the TB-Speed SAM main study. Patient participation in this ancillary study is voluntary; parents will be free to opt out from the Covid sub-study without any consequence on the participation of the child to the main SAM study. Only children whom parents have approved participation to main study will be able to participate in the sub-study.

• Inclusion visit (D0-D3)

The following procedures will be performed during the TB-Speed SAM inclusion visit:

- Questionnaire on Covid-19 contact investigation: parent/guardian will be asked questions regarding the child's exposure to the SARS-Cov-2
- Unless national recommendation for SARS-Cov-2 sample collection is different (Appendix 5), one nasopharyngeal (or oropharyngeal) swab will be collected for immediate SARS-Cov-2 RT-PCR
- > A blood sample collected for diagnosis of SCD if not previously documented
- A DBS collected and stored for further serological testing of the SARS-Cov-2 specific antibodies (IgM and IgG)
- > A stool sample stored for further SARS-Cov-2 RT-PCR (see Table 6).

• Follow-up visits (D15 to M6)

A second DBS will be collected and stored for further serological testing of SARS-Cov-2 at M6.

In children with a negative SARS-Cov-2 RT-PCR at inclusion but showing new symptoms suggesting of Covid during follow-up, another naso/oropharyngeal swab will be collected (see Table 6).

There will be no additional specific follow-up visits for Covid-19 on top of those planned for children enrolled from the main TB-Speed SAM study (see 7.3. Patient schedule).

11.8. Laboratory evaluations

• Biological samples collection

Procedures for sample collection, transportation, and processing at the laboratory will be detailed in specific SOPs. To minimize the risk for participants, collection of naso/oropharyngeal swabs for SARS-CoV-2 detection will be performed either by the study nurses collecting NPA, who will receive specific training, or by specialized staff from the Covid surveillance team according to country policy.

Sample type	Minimal amount required	Laboratory test	D0- D3	M6	D15- M6
1 st naso/oropharyngeal swab ^a	minor (swabbing of the nasal/pharyngeal mucosa surface)	SARS-CoV-2 RT-PCR	х		
Stool sample ^b	1 g	SARS-CoV-2 RT-PCR	Х		
2 nd naso/oropharyngeal swab ^c	minor (swabbing of the nasal/pharyngeal mucosa surface)	SARS-CoV-2 RT-PCR			х
Blood (EDTA or dry tube) ^d	2 mL ^d	Sickle cell disease	Х		
DBS	approximately 50 µL (0.05 mL) collected by finger/heel/toe prick	SARS-CoV-2 serology	Х	х	

^a For young infants (< 6 months) an oropharyngeal swab is preferred due to the small diameter of nasal passage and increased risk of trauma.

^b If the volume of the stool sample collected for the TB-Speed SAM study does not allow for 1) Ultra testing, 2) biobanking, and 3) SARS-CoV-2 testing, an additional stool sample will be collected.

^c The 2nd swab will be collected in children negative for SARS-CoV-2 at inclusion showing new symptoms suggestive of Covid during follow-up.

^d Possibly performed on the same tube than CBC for the SAM study to avoid additional sampling. Volume of blood draw must not exceed 3 ml/kg/visit and 7ml/kg/6 weeks.

The swabs will be referred for immediate testing whenever possible. However, depending on laboratory testing capacities and national policies, it may be possible only for children fitting indication of Covid-19 testing (i.e. meeting suspect case definition, see Appendix 6). If the testing delay is above 72h, the swabs will be stored at -80°C until further testing. The stool sample and the DBS will be stored at the country Central Laboratory to be tested later on.

• RT-PCR for SARS-Cov-2

SARS-CoV-2 virus infection confirmation will be performed by real-time RT-PCR either by inhouse or commercial assays at national Covid-19 Reference Centres, namely (subject to modification depending on laboratory capacities and new accreditations at the time of the substudy implementation): Uganda Virus Research Institute/MRC Center in Entebbe, or Medical and Molecular Laboratories Limited, Makerere University, in Uganda; and Virology Laboratory, UTH, Lusaka, or TDRC Laboratory, Ndola, in Zambia.

• Immunological assays

DBS collected at Day 0 and Month 6 will be sent to the Virology Laboratory, TransVIHMI Research Unit, IRD (Montpellier, France) for testing with the Multiple Analyte Profiling (xMAP) serological screening assay (Luminex Corp. Austin, TX, USA). Recombinant Nucleocapsid (NC) and Spike (S) proteins from human coronaviruses (SARS-CoV1, SARS-CoV2, MERS-CoV) will be used for a large spectrum screening and to evaluate the immune imprints of past infections with the two SARS coronaviruses. In addition, synthetic peptides derived from immunodominant regions of the NC, S and membrane proteins (designed by bioinformatics and through literature searches) will be used to discriminate among known coronavirus infections.

• Diagnosis of sickle cell disease

Sickle cell disease will be diagnosed by haemoglobin electrophoresis according to usual procedures at site level.

11.9. Safety measures

Risk assessment by study activities and recommended infection prevention and control measures will be detailed in specific SOPs.

Study nurses will be equipped with the appropriate PPE following WHO recommendation [84], including:

- Droplets and contact precautions (clinical examination, blood, stool, and DBS collection): gowns, gloves, googles, surgical masks
- For aerosol-generating procedures (NPA and GA collection, samples processing at the laboratory): isolation gowns, long gloves, goggles and high filtration masks

Safety boxes will be provided to dispose contaminated sharps and waste appropriately.

Triple packaging boxes will be provided to ensure biosafety during sample transportation.

12. STATISTICAL DATA ANALYSIS

12.1. Statistical analysis manager

The statistical analysis manager will be the study statistician, based at UBx.

The statistical analysis plan will be written by the study statistician and validated by the coordinating investigators.

12.2. Description of the statistical analysis plan

12.2.1. Analysis of the primary endpoint

We will use logistic regression to develop diagnostic prediction models for TB. We will handle missing data using complete-case analysis, restricting analysis to those children with data available for candidate predictors, and will consider multiple imputation. We will include as candidate predictors characteristics used in previous childhood TB scoring systems and algorithms, characteristics previously described as associated with TB in children with SAM, as well as QFT and abdominal ultrasonography results. We will include as predictors CXR features as assessed by the local reader using the simplified TB-Speed CXR reading tool. We will test various duration of symptoms (>2, >3, >4 weeks) in the models and select the one with the best Akaike Information Criterion (AIC). Alternatively automated LASSO method will be used to select predictors among all study data available for the model.

We will develop different models integrating all predictors, and excluding one at a time tests that may not be available in all resource limited settings such as QFT and abdominal ultrasonography, after discussion with the expert committee. We will obtain final models by stepwise backward selection, using a threshold of 0.135 when incorporating variables with two degree of freedom (QFT: negative, positive, and indeterminate) to maximize the AIC, or 0.157 when all variables had one degree of freedom. We will perform internal validation using bootstrap resampling to quantify model optimism, i.e. the apparent performance of the model minus its true performance, which enables to adjust the model area under the receiver-operating-characteristic curve (AUROC) to its real performance.

We will compare AUROCs of models obtained and select the models with the best discriminative ability and parsimony. We will identify the predicted probability cut-off reaching a sensitivity \geq 80%. Using this cut-off, we will develop associated diagnostic scores by assigning each variable in the models to a predictive score equal to the beta coefficient.

As sensitivity analysis, we will assess diagnostic performance of the score obtained in the different countries, in children with or without HIV-infection to identify potential heterogeneity in score performances between these groups and countries.

Finally we will propose to use the score obtained in a stepwise diagnostic algorithm, including the possible first-step screening prediction score identifying children with presumptive TB, and the diagnostic prediction score for the final TB diagnosis. The stepwise algorithm will be discussed with local clinicians involved in the study to better adapt it for future use in their routine practice.

Results will be reported according to the Transparent Reporting of a multivariable prediction model for Individual Prognosis or Diagnosis (TRIPOD) guidelines for clinical prediction models [83].

The modelling strategy will be definitely elaborated according to prevalence and diagnostic accuracy of the different signs/symptoms collected and tests results. It will be detailed in a statistical analysis plan validated by the SAB.

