4.3. Sample size

Data on reported prevalence of TB in children with SAM from African settings is scarce and heterogeneous, largely depending on diagnostic strategies, case definitions as well as bias inherent to retrospective studies. Prevalence data gathered from the published literature varies from 1.6% to more than 30% in HIV-prevalent, urban tertiary health care hospitals, including Zambia [36], [37]. Hypothesizing an intermediate TB prevalence among children with SAM in participating sites of 15%, we will need a sample size of approximately 720 children, including children with either confirmed or unconfirmed TB, to develop a diagnostic algorithm or score with an expected sensitivity of 80%, an unacceptable sensitivity of 65% (minimal acceptable lower confidence interval limit), and 10% missing data on key predictors entering the model.

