7.3. Patient schedule

Table 4: Patient schedule including specimen collection in children

	Study visits						
	Inclusion (D0)	D3 (+/-2 days)	D15 (+/-2 days)	Month 1	Month 2 (+/-7	Month 3 days)	Month 6
Eligibility criteria	Х	uuyo/	uuyo/		(., ,		
Informed consent	X						
Clinical evaluation ¹	X	Х	Х	x	Х	Х	х
Medical and treatment history	X		X	X	X	X	X
Initial TB assessment	X						
Chest X-Ray	X(○) ²	Result			Х		х
Abdominal ultrasound	X	Result					
Lab assessment:		rtoodit					
- HIV diagnosis ³	0	Result					
- Malaria test	X(○) ⁴	rtooun					
- Complete Blood Count (CBC)	X(○) ⁵	Result		х			
- Transaminases + CRP	Х	Results		Х			
- QFT	Х	Result		(X) ⁶			
Maximal number of tubes collected ^{6,7}	10 (9)			6 (2)			
Maximal volume of blood collected ^{6,7,8}	13 mL (12.5 mL)			4 mL (6 mL)			
NPA	Х			(X)	(X)		
Stool sample	Х	(X)		(X)	(X)		
2 GAs		X(○)²		(X)	(X)		
Xpert MTB/RIF Ultra	Х	Result		(X)	(X)		
Mycobacterial culture (on 2 GAs)		Х		(X)	(X)		
Safety/feasibility/tolerability/ acceptability assessment	Х						
 Biobank (frozen samples): Plasma Whole blood NPA, stool, GA leftovers Urine 	(X) ⁶ X X X						
TB treatment if needed ⁹		0	0	0	0	0	0
TB drug adherence assessment			0	0	0	0	0
Treatment of SAM ⁹	0	0	0	0	0	0	
Treatment and care of co-morbidities if needed ⁹ (HIV infection, other)	0	0	0	0	0	0	0
Nutritional status assessment	0	0	0	0	0	0	0
TB treatment response				1			0

 \circ Routine care

X Research

(1) Content of clinical evaluation varies with the visit

(2) Performed as part of routine care in case of TB suspicion

(3) Performed if not available in the patient medical chart

(4) Possibly performed as part of routine care in case of clinical suspicion of malaria

(5) Possibly performed as part of routine care for anaemia assessment

(6) In children <18 months weighing <5 kg, or children presenting with signs of severe anaemia (conjunctival or palmar pallor): QFT test will be performed at M1 and plasma sample for biobank will not be

collected, except in children with signs of severe anaemia if they will benefit from blood transfusion; QFT test will be preferably done just before transfusion. Plasma sample for biobank will not be collected

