³ unable to drink or breastfeed; vomits everything; has had convulsions (more than one or prolonged >15 min); lethargic or unconscious; convulsing now [53].

- 1 NPA, collected by the nurse on the day of admission without prior nasal instillation (see Appendix 3);
- 1 stool sample, collected as soon as the child is able to produce stool (see Appendix 4);
- 2 GAs.

NPA and GAs will be done under SpO2 monitoring. They will not be attempted in children presenting severe respiratory distress or SpO2 <90% under appropriate oxygen therapy, severe dehydration or features of shock. Advice will be sought from a clinician not directly involved in the study to make the determination on a case by case basis for very sick children.

The safety of bacteriological specimen collection (NPA and GA) will be assessed by study nurses. Contraindications, implementation of sample collection procedures, and safety monitoring during collection will be detailed in study procedures.

The feasibility and tolerability of NPA will be assessed using qualitative and quantitative tools (Cf Chapter 7.6) in a sub-group of children.

Bacteriological tests performed on collected specimen are detailed in Chapter 8.2.

Additionally, a urine sample will be collected for biobanking.

Extra tests not planned by the protocol will be requested by the clinician in accordance with his/her practice and the national recommendations.

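### Complete-case analysis is the main missing-data method although the protocol defers QFT, a candidate predictor, to Month 1 in small and severely anaemic children, so those who die or are lost early leave the model

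*Protocol*

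**What the plan says.** Section 12.2.1 of the protocol sets the rule for the primary model: "We will handle missing data using complete-case analysis, restricting analysis to those children with data available for candidate predictors, and will consider multiple imputation". It names no condition that would bring imputation in. The candidate predictors there include clinical characteristics, chest X-ray features from the local reader, "as well as QFT and abdominal ultrasonography results". Models are then built with all predictors and with tests such as QFT or ultrasound left out one at a time. Their AUROCs are compared, and a cut-off is chosen that reaches a sensitivity of at least 80%.

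Two rules elsewhere decide who has results:

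- Table 4, note 6 (section 7.3): for children under 18 months weighing less than 5 kg, or with signs of severe anaemia, "QFT test will be performed at M1". Anaemic children due for transfusion are excepted; their sample is preferably taken just before it. Table 5a (children under 18 months) repeats the deferral. Table 5b (children over 18 months) shows QFT at inclusion only, so it is unclear whether the anaemia clause of note 6 reaches older children. These places must be reconciled.
- Section 7.4, on nasopharyngeal and gastric aspirates: "They will not be attempted in children presenting severe respiratory distress or SpO2 <90% under appropriate oxygen therapy, severe dehydration or features of shock".

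Section 4.3 treats missing predictors as a loss of numbers: "we will need a sample size of approximately 720 children", allowing for "10% missing data on key predictors entering the model".

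**The concern.** Complete-case analysis is harmless when the children with full data resemble those without. Here the protocol's own rule ties the timing of QFT to low weight and anaemia. Deferral becomes permanent absence when the child dies or is lost in the first month, and section 16.1.1 says that death is common in SAM, especially with TB or HIV. The loss therefore plausibly depends on the outcome being predicted as well as on baseline severity.

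The score is meant for all hospitalised children with SAM. If coefficients and cut-off come from larger, less sick survivors, the sensitivity and specificity that form the primary endpoint may not apply to the children at highest risk.

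Deferred children who do reach Month 1 raise a second question. Section 7.5 plans TB diagnosis for Day 0 to Day 3, with immediate treatment after a positive Ultra. A Month 1 QFT was not available at that decision and may have been drawn on treatment.

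**Working it through.** **1. Reproducing the planned size.** Inputs from section 4.3: "Hypothesizing an intermediate TB prevalence among children with SAM in participating sites of 15"%; sensitivities given as "an expected sensitivity of 80%, an unacceptable sensitivity of 65% (minimal acceptable lower confidence interval limit"; 10% missing. Alpha and power are not stated. Assume an exact one-sided 5% test of 65% with at least 95% power at 80%.

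- Smallest number of TB cases: 98 (at least 72 of 98 detected; power 0.955).
- Children: 98 / 0.15 = 653.3, so 654.
- Inflation: 654 × 1.10 = 719.4, so 720; or 654 / 0.90 = 726.7, so 727.

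The stated 720 reproduces. One-sided 2.5% with 90% power also comes close: 96 cases, 640 children, 640 / 0.90 = 711.1, so 712.

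**2. What missing data do to precision.** Cases in 720 children: 720 × 0.15 = 108. The protocol gives no missing share for any test, so a range is assumed. Power is for the exact one-sided 5% test of 65% when true sensitivity is 80%. The lower limit is the exact two-sided 95% limit when about 80% of cases are detected.

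| Missing | Cases left | Power | Lower limit |
|---|---|---|---|
| 10% | 97 | 0.94 | 0.711 |
| 20% | 86 | 0.92 | 0.702 |
| 30% | 76 | 0.89 | 0.695 |
| 40% | 65 | 0.86 | 0.682 |

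Even with 40% missing the lower limit stays above 65%. Loss of numbers is not the main problem.

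**3. What selection could do.** The cut-off is chosen to reach at least 80% sensitivity in the children analysed. Take 80% there, let a share m of TB cases be excluded, and let sensitivity among them be s. Whole-cohort sensitivity is (1 − m) × 0.80 + m × s. Both m and s are assumptions; s = 0.50 to 0.70 is used to show scale.

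- m = 0.10: 0.72 + 0.05 to 0.07 = 77% to 79%.
- m = 0.20: 0.64 + 0.10 to 0.14 = 74% to 78%.
- m = 0.30: 0.56 + 0.15 to 0.21 = 71% to 77%.

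If s were also 80% there would be no shortfall. The protocol does not give the share of children under 5 kg, the share with untransfused severe anaemia, or the expected losses before Month 1, so neither m nor s can be fixed. Inflating the sample leaves m and s unchanged and so cannot remove the shortfall.

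**The case against.** The strongest reply is statistical. If missingness depends only on covariates in a correctly specified logistic model, and not on the outcome given them, complete-case coefficients are consistent. The deferral rule uses weight and anaemia, which are recorded. This stands for deferral itself. It does not cover death or loss before Month 1, which may depend on TB, nor a final model from which selection has removed weight or anaemia. Nor does it make a cut-off and accuracy estimated in survivors apply to everyone.

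Section 12.2.1 also keeps imputation open and leaves modelling detail to the analysis plan. That excuses the missing imputation details, but not the choice of complete-case analysis as the default.

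Four stronger readings are tempting, and the document does not support them:

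- *Models with and without a test use different children.* Section 12.2.1 does not say whether completeness is judged once over all candidates or model by model. Only the ambiguity is established.
- *A Month 1 QFT enters as an admission value.* Nothing says so; the protocol is silent on which QFT is used.
- *Children without aspirates are dropped.* Section 12.2.1 does not name aspirate results among its predictors, and gastric aspirates serve the reference standard. Ultra on NPA is among the tests assessed for added value (section 2.2), so its absence could matter if used. But children are enrolled after stabilisation (7.2), a failed NPA is retried (7.8.1), and Ultra is also run on stool (8.2.2).
- *The 10% allowance is far too small.* Six tests each 95% complete and independent would give 0.95^6 = 0.735, or 529 children and 79 cases. Independence conflicts with the argument that gaps cluster in the same sick children. With the three tests that 12.2.1 names, 0.95^3 = 0.857, about 617 children and 93 cases, close to the 97 planned. At 98% completeness, six tests give 0.98^6 = 0.886.

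**Conclusion.** The point holds in a limited form. The protocol makes complete-case analysis its main method while its own schedule makes QFT late, and in early deaths and losses absent, in small infants and in untransfused children with signs of severe anaemia. Missing completely at random is not plausible for this predictor, and the sample-size allowance addresses numbers only.

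The size of the bias is unknown. The 71% to 79% sensitivities above are illustrations under assumed values, not estimates. The effect on precision is modest (power about 0.94 at 10% missing, 0.89 at 30%), under a one-sided 5% test that the protocol does not state. Missing NPA results may add to the problem but are the weaker example. The choice should be changed before the analysis; it does not undermine the study design.

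**What to change.** In section 12.2.1:

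1. Make multiple imputation of predictors the main analysis, with an imputation model that includes the outcome, weight, age, anaemia, HIV status, site and severity signs, combined with the bootstrap validation. Keep complete-case analysis as the sensitivity analysis.
2. Treat a QFT not taken at baseline and before TB treatment as missing at baseline, and impute it, instead of substituting the Month 1 value.
3. Compare models with and without a test on one common set of children, and say so.

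Separately, reconcile Table 4 note 6 with Tables 5a and 5b on which children have QFT deferred, so that the expected pattern of missing data is clear.

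The cost is wording and more computing; no new data are needed. The downside is reliance on missing at random given the recorded variables, which the complete-case sensitivity analysis helps to gauge but cannot prove.
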